1.3 Research Design and Methods

This pilot study is a 2-arm individually randomized controlled trial design in which outcomes of MMT patients randomized to MORE are compared to outcomes of those randomized to treatment as usual (TAU). In the pilot study (R21; N=31), we will randomize MMT patients with chronic pain to MORE (n=15) or TAU (n=16). This study phase will focus on establishing study feasibility in recruiting, retaining, and following up study participants before progressing to a larger Phase II clinical trial (R33, N=150). Participants with pain who are receiving MMT for an opioid use disorder (OUD) will be recruited from the New Brunswick Counseling Center (NBCC) and the Lennard Clinic.

A. *Describe, in order of occurrence, all research procedures being performed, when and where they are performed, and by whom (including procedures being performed to monitor subjects for safety or minimize risks).*

Participants will be recruited through flyers posted in the clinics, being approached by research assistants in the waiting room of their usual methadone clinic (New Brunswick Counseling Center or Lennard Clinic), and referral by clinic staff. The number of individuals who contact the study staff through the flyers or referral and who are approached by study staff in the clinics will be tracked. Number of individuals who refuse study participation and who consent to the study will also be tracked. If an individual is interested in study participation, a trained research assistant will lead the individual through the informed consent process in a private space.

Participants randomized to the MORE condition will participate in eight, weekly, two-hour group sessions led by a clinic or study counselor. Each session will contain 4-8 participants and take place in a private room at the New Brunswick Counseling Center (NBCC) or the Lennard Clinic. Attendance at each session and reasons for missing sessions will be recorded. Participants randomized to the control condition will continue receiving treatment as usual at the NBCC.

All study participants will partake in a total of three interviews lasting up to 90 minutes and occurring at baseline, 8- and 16- weeks post-baseline in a private room at NBCC or the Lennard Clinic. Each participant will also have a urine or saliva sample collected during each assessment. This is required to verify self-report of drug use. Due to social desirability, it is common for people to not accurately report drug use; therefore, biochemical verification is the gold standard measure of drug use. All attempts to reach participants to schedule follow-up assessments will be tracked. Participants will also complete cognitive testing (for approx. 30-45 minutes) at baseline and 8-weeks and ecological momentary assessments (EMA) conducted via smartphones, which will be provided to each participant by study staff. EMA participation will require the participant to respond to twice-daily prompts in which they will be asked a series of brief questions regarding their current mood and exposure to opioid triggers. Additionally, subjects will be asked to initiate responses when they experience serious craving or relapse to opioid use. Each EMA assessment will last approximately 3-5 minutes.

B. What data points will be collected including long-term follow-up?

All study participants will participate in three face-to-face assessments at baseline, 8-weeks, and 16-weeks. If participants are unable or unwilling to attend a research appointment at their clinic, a research assistant will conduct a telephone interview. Information will be collected on demographic characteristics, substance use, methadone treatment, opioid craving and withdrawal, physical pain, non-reactivity, negative and positive affect, attentional bias, cognitive and mental health, physical health, and intervention implementation and attitudes. At the baseline and 8-week research visits, participants will complete three cognitive tasks on a computer that assess inhibitory control, implicit (automatic) associations, and the precedence of global features in visual perception. Urine and/or saliva samples will be requested at each assessment for confirmation of self-reported drug use. In addition, participants will partake in daily ecological momentary assessments (EMA) throughout the 16-weeks of study participation that include brief measures of pain intensity, mood, and substance use. Additionally, participants will be asked to initiate communication via smartphone when they either lapse to opioid use or experience serious craving. Self-initiated responses will include information about the circumstances surrounding their craving/lapse. A synopsis of all study instruments are included below (see 1.9B – Study instruments).

C. Define the duration of the study and the length of time each subject will participate in the study.

This pilot study is expected to take one year. Each subject will participate in the study for a total of 16-weeks.

Describe any primary and secondary study or safety endpoints

Feasibility will be assessed according to recruitment, retention and follow-up benchmarks. We will consider recruitment and retention efforts successful if we are able to enroll 75% of our target enrollment (31 participants) within a period of 4 months. Although we expect to recruit 100% of our planned sample by month 7, we set the criterion at 75% because we could adapt strategies for the next study to increase recruitment (including adding more MMT sites), if necessary. Retention will be considered successful if 50% of participants attend at least 4

MORE sessions. We will consider our ability to follow participants successful if we obtain 8-week assessments from at least 65% of participants and 16-week assessments from at least 50%. Although we are targeting a follow-up rate in both groups of at least 80% and 75% at 8 and 16 weeks, respectively, we set the benchmarks at 65% and 50% because, again, if necessary, we can adapt follow-up strategies for the next study, based on lessons learned in this study.

Preliminary outcome measures to be assessed during this pilot study will be time until opioid lapse and MMT dropout. Preliminary secondary outcomes will be: days of methadone medication use, days of opioid and other drug use, and changes in pain severity and intensity. Additional measures are described below.

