1.8 Primary Specimen Collection

A. *What types of specimen will be collected, where, and by whom?*

We will utilize a urine or saliva screen that tests for buprenorphine and methadone (to provide corroboration of MAT engagement and compliance) and additional substances (e.g., benzodiazepines, barbiturates, cocaine, marijuana, methamphetamine, morphine, oxycodone, phencyclidine and amphetamine). These specimens will be collected by study research assistants at baseline and each follow-up time point (8-weeks and 16-weeks).

Biochemical verification of self-report opioid relapse and other drug use is the gold standard measurement of drug use and, without biochemical verification, self-reported drug use as an outcome variable will be questioned by the scientific community.

B. *How will the specimens be transported and by whom?*

The sample will be collected and results read at the time of sample collection. The sample will be disposed as soon as results are read (typically within 10 minutes of sample collection) and recorded. The sample will not be transported. Samples will be collected and read in a private area where others will not be able to see or hear the results.

C. *Who will process the specimens?*

Research assistants will process the sample.

D. *How long will the specimens be kept?*

The sample will be disposed of immediately after results are read and recorded.

E. *How will the specimens be destroyed upon study completion?*

Samples will be flushed down the toilet (urine test) or disposed of in the trash (saliva test).

F. *If specimens will be banked for future use, what will be the process for providing investigators with access to the bank and how will this be tracked?*

N/A

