1.9 Interviews, Focus Groups, or Surveys

A. Administration

■ Timing and Frequency

Research staff will collect interview data and drug screens from both intervention and control group subjects through face-to-face standardized measures conducted at baseline and either phone or face-to-face measures 8- and 16- weeks post baseline. Cognitive testing data will be collected at baseline and 8-weeks. If the research assessments are conducted over the phone, cognitive assessments and drug screen results will be considered missing data. Additionally, subjects will engage in twice-daily EMA assessments of approximately 3-5 minutes each. Subjects will also initiate EMA communications to report lapses or serious cravings, which will also last for under 5 minutes.

■ Location

The assessments and drug screens will take place in private rooms at the New Brunswick Counseling Center (NBCC) and Lennard Clinic.

■ Procedures for Audio and Visual Recording

Audio or video recordings will be made of the MORE therapy sessions and the recordings will be transcribed research staff. All recordings will be stored in password protected computers, in a locked office at [name], in password protected files, on the Rutgers network.

B. Study Instruments

Feasibility Outcomes:

- The number of individuals who express interest in the study and the number who refuse (and reasons for refusal) will be tracked in a log.
- The number of individuals who contact the staff with interest in the study will be tracked in a log.
- The number of individuals screened and eligible/ineligible will be tracked in a log.
- The number of individuals consented will be tracked in a log.
- The number of individuals who refuse participation after/during consent process will be tracked in a log.
- The number of sessions completed by study participants will be tracked in a log.
- The number of participants who drop out and reasons for drop out will be tracked in a log.
- Reasons for missed sessions will be tracked in a log.
- The number of completed/missed assessments will be tracked in a log.

Exploratory outcomes among participants in the MORE condition relative to treatment as usual (TAU) in regard to opioid use outcomes such as:

- Time until first opioid lapse assessed through ecological momentary assessment data and timeline follow-back.

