substances (benzodiazepines, barbiturates, cocaine, marijuana, methamphetamine, morphine, oxycodone, phenyclidine and amphetamine). At each research visit we will conduct a timeline follow-back³ with each participant to account for missing EMA drug use data. The timeline follow-back is a reliable and valid measure where participants are asked to recall and record events (e.g., drug use) within a specified time period on a calendar. We will combine self-report of opioid relapse and other drug use with biochemical measures because it is the gold standard, and without biochemical verification, self-reported drug use as an outcome variable will be questioned by the scientific community. If a biochemical measure is negative, but the participant reports drug use, the participant will be coded as using drugs since the biochemical measure will only capture a specific time point. However, if the participant self-reports drug abstinence, but the biochemical measure is positive for drug use (the more likely scenario) the participant will be coded as having used drugs.

Craving (Baseline, 8 weeks, and 16 weeks). Opioid and other drug craving will be assessed with an adapted version of the Penn Alcohol Craving Scale (PACS)⁴ and the Craving Suppression Scale. The PACS is a valid, reliable, and internally consistent measure that consists of five self-report items that have been found to predict relapse. The items assess the intensity, frequency, ability to resist, and duration of craving. Originally developed to assess alcohol craving, it has been adapted and used to measure craving for various substances, including opioids,⁵ and adapted versions have been used in trials of mindfulness-based interventions for substance use.⁶ The Craving Suppression Scale is a 17 –item measure that assesses how individuals cope with craving

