Opioid/Natural Reward, Implicit Association Task (IAT; Baseline, 8-weeks): The IAT is a widely-used cognitive-behavioral paradigm that measures the strength of automatic (implicit) associations between concepts in people's minds relying on latency measures in a simple sorting task.²² Participants are asked to, on a computer, categorize attributes (e.g. "pleasant"; "unpleasant") and target items (e.g. "friends" vs. "pills") into predetermined categories via keystroke presses. The basic task is to press a left key (E) if an item (e.g. "pleasant") belongs to the category presented on the left (e.g. "Good") and to press the right key (I) if the word (e.g. "unpleasant") belongs to the category ("Bad") presented on the right. For practice, participants sort items into the target categories "Opioids vs. Natural Reward" and the attribute categories "Good vs. Bad". For the test, participants are asked to sort categories into the paired/combined categories (e.g. "Natural Reward OR Good" on the left vs. "Opioid OR Bad" on the right). Pairings are reversed for a second test (e.g. "Opioid OR Good" on the left vs. "Natural Rewards OR Bad" on the right). Block order is counterbalanced by group number. A d-score will be derived from the implicit association task.

Precedence of Global Features in Visual Perception, Global Local Task (Baseline, 8-weeks): On a computer, participants are briefly presented with letter shapes (e.g. H or S) that are made up of little letter shapes (e.g. H or S).²³ Some of these letters have the same global (overall shape) and local (individual building shapes) letters (e.g. an H that consists of Hs), and some have different global and local letters (e.g. an H that consists of Ss). In the global condition participants are asked to respond to the global shape of the letter (e.g. press key H if the global shape of the letter is an H regardless of individual building blocks); in the local condition participants are asked to respond to the local shapes of the letter (e.g. press H if the local building elements are Hs regardless of overall shape). The number of errors during the last block of the global/local task will provide a shifting attention score.

Intervention implementation (Week 8). Number of sessions completed and missed will be assessed for each participant in both conditions. Reasons provided for missed sessions will also be recorded.

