4.3 Subject Randomization

Since MORE is a closed group, we will randomize cohorts of 10-16 participants (depending on speed of recruitment) at each site to TAU or MORE with block randomization. Once we recruit at least 10 participants at a particular clinic, we will randomize participants to MORE or TAU, and the MORE group will begin. We estimate that we will recruit at least 10 participants per month.

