4.6 Consent Procedures

A. Consent

- **Documenting Consent**

If you will document consent in writing, provide a list of each document here and upload your consent document(s) in eIRB. For guidance see HRP-091.

Consent for Study Participation

- **Waiver of Documentation Of Consent**

N/A

- **Waiver or Alteration of Consent Process**

- (i) **Waiver or Alteration Details**

N/A

- (ii) **Destruction of Identifiers**

N/A

- (iii) **Use of Deception/Concealment**

N/A

B. Consent Process

- **Location of Consent Process**

The informed consent process will take place at NBCC or the Lennard Clinic, in a private room reserved for the research study to take place.

- **Ongoing Consent**

N/A

- **Individual Roles for Researchers Involved in Consent**

The role of the individuals listed in the application as being involved in the consent process.

Study recruiters/research assistants, who have been trained in the study protocol and the process for obtaining consent, will consent subjects for the study.

- **Coercion or Undue Influence**

Those who choose to participate will complete a written, informed consent process before any study procedures are performed. A signed copy of the informed consent will be given to the study participants. Research staff will read the consent form out loud to any individuals who are unable to read the consent form on their own. Topics covered in the consent form will include a description of study procedures, the time involved, the right to withdraw at any time without penalty, procedures used to protect participant anonymity, information on the use of data, the potential benefits and risks of participating in the study, and limits of confidentiality regarding expressions of suicidal ideation, homicidal ideation, or a child at risk. Research staff will be trained to note signs that suggest that the individual is unable to consent and will: 1) ask permission from the individual before questioning him/her; 2) observe for signs of illness, intoxication, and other reasons causing individuals to be unable to consent; 3) assess orientation to person, place, time, and situation; and, 4) ask the potential participant to paraphrase the study requirements.

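### Allocation is not kept from the research assistants who take the timeline follow-back and read the drug screen, which may bias the exploratory drug-use estimates

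*Combined protocol and SAP*

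**What the plan says.** **Who assesses.** Under 1.9 A, research staff collect interviews and drug screens in both arms. Under 1.3 B, a research assistant interviews by telephone when a participant does not come in. A timeline follow-back is taken at each research visit to cover missing EMA drug-use data (1.9 B, current substance use).

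**The screen.** "Each participant will also have a urine or saliva sample collected during each assessment" (1.3 A). Research assistants collect and process it on the spot, and "The sample will be disposed as soon as results are read (typically within 10 minutes of sample collection) and recorded" (1.8 B). If the screen is positive and the participant reports abstinence, "the participant will be coded as having used drugs" (1.9 B). Reported use with a negative screen is also coded as use. Telephone assessments have no screen (1.9 A).

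**Allocation.** Section 4.3 says only that "we will randomize cohorts of 10-16 participants (depending on speed of recruitment) at each site to TAU or MORE with block randomization". It does not say who holds the result or from whom it is withheld.

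**Tasks that can reveal the arm.**
- Assessments include items on intervention implementation and attitudes (1.3 B).
- "Audio or video recordings will be made of the MORE therapy sessions and the recordings will be transcribed research staff" (1.9 A).
- "Number of sessions completed and missed will be assessed for each participant in both conditions" (1.9 B, week 8).
- Only MORE participants receive a $5 card per session, and the incentive log names the staff member who pays (4.8 B and C).
- A research assistant prepares monthly summaries of all data (6.1 D, 6.3 F).

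**The concern.** The plan treats biochemical verification as the safeguard against misreported drug use. That safeguard is one reading by one person, who may know the arm, of a sample that is then thrown away. The follow-back is led by an interviewer and is used where the participant's own smartphone record is absent. An assistant who knows the arm could probe harder, accept a denial more readily, or read a faint line differently. The direction cannot be predicted. At stake is the MORE-TAU difference in drug use. Section 6.1 B says the pilot is to give a preliminary effect size and inform a larger study, and 1.3 puts that study at N=150.

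**Working it through.** The plan states no error rate, event rate or power for these outcomes, so there is no figure to reproduce. The check has two parts.

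**1. Which outcomes can be reached**
- *Time to first lapse and days of use* come from EMA plus timeline follow-back (1.9 B). Probing can act on both, chiefly where EMA is missing. Where EMA was answered, the two sources can be compared.
- *The screen* gives no lapse date and no day count, and 1.9 B does not say how a positive result enters either outcome. Because reported use is always coded as use, a reading matters only for someone reporting abstinence, and only at an in-person visit.
- *MMT dropout and methadone days* come from clinic records (1.9 B), so neither the interview nor the screen reaches them.
- *Progression milestones* are recruitment, session attendance and follow-up rates (1.1 B, 1.3 C). None uses drug-use coding.

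**2. Leverage of one re-coded participant**

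Inputs: arms of 15 and 16 (1.3, 1.5) and follow-up benchmarks of 65% and 50% (1.3 C). Use proportions of 30% to 70% are assumptions. The shift is 100/n points. The standard error (SE) of the difference is √[p(1−p)(1/n₁ + 1/n₂)], at p = 0.3 (same as 0.7) and p = 0.5.

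| Follow-up | MORE / TAU | Shift from one re-coding | SE of difference | Shift ÷ SE |
|---|---|---|---|---|
| Full | 15 / 16 | 6.7 / 6.3 points | 16.5 to 18.0 points | 0.35 to 0.40 |
| 65% (9.75, 10.4) | 10 / 10 | 10.0 points | 20.5 to 22.4 points | 0.45 to 0.49 |
| 50% (7.5, 8) | 8 / 8 | 12.5 points | 22.9 to 25.0 points | 0.50 to 0.55 |

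Two re-codings in one arm double these, to about 0.7 to 1.1 SE.

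**Effect on a test.** Starting from 5/10 in each arm, re-coding two MORE participants as non-users gives a 20-point difference (Fisher p = 0.65), and three give 30 points (p = 0.35). With 15 and 16 participants and use near 30%, 50% or 70% (4/15 v 5/16, 8/15 v 8/16, 10/15 v 11/16), it takes 4, 7 and 6 re-codings to pass p < 0.05.

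**Average bias under assumed rates.** Bias = proportion using × share of users who deny use × between-arm difference in detecting them.
- Low: 0.3 × 0.3 × 0.1 = 0.9 points.
- High: 0.5 × 0.5 × 0.3 = 7.5 points.

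None of these three factors is given in the documents.

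**The case against.** The case on the other side is substantial.

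- **These outcomes are exploratory and declared unpowered.** This stands. The milestones that govern progression do not depend on drug-use coding, and the larger trial's N is already stated. It lowers the priority but does not remove bias from an effect size the plan says it will use.
- **EMA is entered by participants without an interviewer.** This stands as a partial check. It does not help on unanswered days, which are the days the follow-back is there to fill.
- **Exposure of the assessors is partly inferred.** This also stands. The plan says research staff transcribe recordings, not that the assessors do. Attendance is already kept in a log and need not be asked at the visit. The firmer routes are the attitude items in the assessment and the MORE-only session payments.
- **Existing safeguards.** Independent form review (6.1 D), staff training (2.2) and standardized measures (1.9 A) help data quality. None hides the arm or allows a discarded screen to be re-read.

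A reader might infer that the drug-use data as a whole cannot be checked, that a screen-confirmed use endpoint is compromised, or that a few misreadings could create a significant result. The documents do not support these. Only the screen reading is beyond recheck, screen-confirmed use is not a listed outcome, and the Fisher figures show that several re-codings would be needed. Nor do the documents say that one person does all the tasks; they simply do not separate them.

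**Conclusion.** The point holds in a limited form. No available text masks the staff who conduct the follow-back and read the screen, and planned tasks can show them the arm. Time to lapse and days of use are open to biased probing, mainly on days without EMA. Screen-based coding is open to biased reading only for reported abstainers seen in person. One re-coded participant is worth 6 to 7 points of an arm's proportion with full follow-up and about 10 to 12.5 points at the benchmarks. This is leverage, not an estimate of how often it will happen. It is computed on a simple proportion, whereas the listed outcomes are a time and a day count. The consequence is a possibly biased exploratory effect size, not a wrong progression decision. I would rate it as something to consider.

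**What to change.** Add the following to 1.3 A and 1.9 A.

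1. **Task separation, where a clinic has more than one existing assistant.** The assistant doing a cohort's follow-up interviews and screens does not receive its allocation, keep its session log, pay its session incentives, transcribe its MORE recordings or prepare summaries by arm.
2. **At every visit, in every clinic.**
   - Take attendance from the log.
   - Give intervention attitude items last, after the follow-back and screen are recorded, or have another staff member give them.
   - Ask participants not to mention their group.
   - Have the assessor note whether the arm became known, and report that count by arm.
3. **Where one assistant covers a clinic.** Apply step 2 and report assessment there as unmasked.

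I would not ask for the screen to be read before the interview, since that gives the interviewer the result ahead of the follow-back and opens another route to selective probing.

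The cost is protocol wording and a less flexible rota, with no new post. Some unmasking will remain, and the screen reading itself stays uncheckable. A second reader or a photograph would address that, but it is an added procedure I would not press for exploratory outcomes. The unmasking count is useful in itself, because it tells the larger trial whether masked assessment is workable in these clinics.
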